6.6.7. Sample Collection

The procedures for the collection, handling, and shipment of laboratory samples are specified in the Laboratory Manual supplied to sites by the central laboratory.

6.7. Committees

6.7.1. Independent Data Monitoring Committee (DMC)

A DMC will be utilized in this study to ensure external objective medical and/or statistical (if needed) review of safety data in order to protect the ethical and safety interests of subjects. The DMC will review unblinded aggregate (and, where necessary, individual) subject safety data at pre-defined intervals according to a DMC charter. The analysis plan for the DMC review will be described in the DMC charter, which will also contain details of the composition and the responsibilities of the DMC.

6.7.2. Clinical Endpoint Committee (CEC)

An independent CEC will review and adjudicate all suspected recurrent pericarditis events that occur during the RW period of the study. The procedures for adjudicating events will be described in the CEC Charter. This will be done independent of the Investigators, and in a manner blinded to treatment assignment. The CEC will complete assessments on an ongoing basis.

7. STATISTICAL AND ANALYTICAL PLAN

7.1. Primary Efficacy Endpoint

The primary efficacy endpoint is time to pericarditis recurrence, defined as the time from randomization to the date of the first pericarditis recurrence for each subject. Only CEC-confirmed pericarditis recurrence will be considered as an event for the primary analysis.

A sensitivity analysis will be done based on the Investigator's assessment of the event.

Pericarditis recurrence is defined in Section [6.2.3](#).

Subjects who do not have a pericarditis recurrence will be censored at the date of the last available assessment for pericarditis recurrence during the RW period before data cutoff. Detailed censoring rules will be specified in the Statistical Analysis Plan (SAP).

7.2. Secondary Efficacy Endpoints for the RW Period

This Section defines secondary efficacy endpoints for the RW period. Endpoints for the RI period and for the LTE are defined in Section [7.3](#).

7.2.1. Major Secondary Efficacy Endpoints

- Proportion of subjects who maintained Clinical Response at Week 16 of the RW period. Clinical Response is defined as a weekly average of daily pericarditis pain on the 11-point NRS ≤ 2.0 and CRP level ≤ 0.5 mg/dL, and on monotherapy of randomized study drug at Week 16.
- Percentage of days with no or minimal pain in the first 16 weeks of the RW period. No or minimal pain is defined as non-missing NRS ≤ 2 .
- Proportion of subjects with absent or minimal pericarditis symptoms (based on the 7-point PGIPS) at Week 16 of the RW period.

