3.1.3. Double-blind Placebo-controlled RW Period (pericarditis recurrence event-driven duration)

During the RW period, subjects who were able to stop background pericarditis medications and who achieve Clinical Response on rilonacept monotherapy at RI Week 12/RW baseline will be randomized 1:1 to double-blinded administration of study drug:

- Rilonacept 160 mg (or 2.2 mg/kg in pediatric subjects ≥ 12 and < 18 years old) SC injections once weekly OR
- Matching placebo SC injections once weekly

Pericarditis Recurrence in the RW Period: For the definition of pericarditis recurrence, refer to Section 6.2.3.

Upon pericarditis recurrence, subjects who report at least 1 day with pericarditis pain measurement ≥ 4 on the 11-point Numerical Rating Scale [NRS] and have 1 CRP value ≥ 1 mg/dL (either on the same day or separated by no more than 7 days) will receive **bailout rilonacept** (2 open-label injections of 160 mg rilonacept [or 4.4 mg/kg for pediatric subjects]) irrespective of randomized treatment assignment and as soon as at least 5 days have passed since the last study drug injection. The subjects transitioning to bailout rilonacept will remain blinded to their prior RW period treatment assignment. Sequential Oral Rescue Therapy (ORT), i.e., analgesics first, then NSAIDs, and then colchicine, can be added, if needed, at the discretion of the Investigator, as outlined in Section 5.6.3 and detailed in the Pharmacy Manual.

Subjects with pericarditis recurrence who do not meet the protocol criteria for bailout rilonacept will continue blinded study drug until they meet the protocol criteria for bailout rilonacept or through the end of the RW period. For those subjects, sequential ORT can be added to blinded study drug at the discretion of the Investigator, as outlined in Section 5.6.3 and detailed in the Pharmacy Manual.

All suspected pericarditis recurrence events in the RW period will be formally adjudicated by the Clinical Endpoint Committee (CEC), and only events that are confirmed by the CEC as pericarditis recurrences will be used in the Primary Endpoint analysis.

The RW period will continue until the prespecified number of primary efficacy endpoint (CEC-confirmed pericarditis recurrence) events has occurred. Based on projected event accrual and subject randomization, Kiniksa Pharmaceutical will determine the end of the RW period and announce to sites so that subject End of Randomized Withdrawal (EORW) visits

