3.3. Justification for Dose Selection

[REDACTED]
[REDACTED] i.e., 320 mg SC loading dose (4.4 mg/kg in subjects ≥ 12 and < 18 years old), followed by once-weekly SC doses at 160 mg (2.2 mg/kg in subjects ≥ 12 and < 18 years old).

In the rilonacept development program in CAPS, gout, rheumatoid arthritis, and other inflammatory conditions, over 2000 subjects were exposed to rilonacept, including 1650 subjects receiving a rilonacept dose of 160 mg or higher. A total of 103 and 169 subjects were exposed to any rilonacept dose for at least 1 year or 6 months, respectively. Most of the real-life experience with rilonacept comes from the CAPS population treated at this marketed dose. As of March 2018, approximately 365 CAPS patients have been exposed to rilonacept in the post-marketing setting since 2008. The safety data accumulated so far support the benefit/risk ratio for the rilonacept dose intended to be evaluated in subjects with recurrent pericarditis.

Based on the clinical data with rilonacept from the Phase 2 proof of concept study (KPL-914-C001), it is expected that rilonacept doses [REDACTED] (320 mg followed by 160 mg SC once weekly and corresponding pediatric doses), and evaluated in the KPL-914-C001 study, will consistently provide adequate suppression of clinical inflammatory response, including CRP levels, in patients with recurrent pericarditis.

Subjects who meet the protocol criteria for **bailout rilonacept** upon pericarditis recurrence in the RW period of the study (Sections 3.1 and 6.2.3), irrespective of treatment assignment at randomization, will receive open-label rilonacept (loading dose of 320 mg SC followed by once-weekly SC injections of 160 mg, or the corresponding pediatric doses). [REDACTED]

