5.7. Method of Blinding

In the single-blind RI period, all subjects will receive rilonacept but will be blinded to the duration of the RI period and the timing of randomization. The RW period is a double-blind period in which rilonacept and placebo are identical in appearance. Neither the subject nor any of the Investigator/site staff, [REDACTED] or Sponsor staff who are involved in the treatment or clinical evaluation of the subjects will be aware of the treatment received (International Council for Harmonisation [ICH] E9).

In the event of a pericarditis recurrence that meets the criteria for bailout rilonacept (Sections 3.1 and 6.2.3), the subject will be transitioned to open-label rilonacept but will remain blinded to their prior RW treatment assignment.

If the treatment allocation for a subject becomes known to the Investigator or other study staff involved in the management of study subjects, the Sponsor and [REDACTED] must be notified immediately. The Investigator may unblind a subject's treatment assignment only in the case of an emergency, when knowledge of the study drug is essential for the appropriate clinical management or welfare of the subject. In most cases, the management of a medical emergency would be the same, regardless of whether the subject received active drug. The treatment assignment will be unblinded through the IWRS.

The [REDACTED] PHV staff may unblind the treatment assignment for any subject with an SAE. If the SAE requires that an expedited regulatory report be sent to one or more regulatory agencies, a copy of the blinded report may be sent to clinical Investigators in accordance with local regulations.

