6.2.3. Management of Suspected Pericarditis Recurrence in the RW Period

Pericarditis Recurrence Definition: Pericarditis recurrence, for the purpose of the protocol, is defined as the recurrence of typical pericarditis pain associated with supportive objective evidence of pericarditis.

At any time point during the RW period, subjects who experience suspected recurrence of their pericarditis will have been instructed to inform their site Investigator as soon as possible. Subjects who experience a suspected recurrence of pericarditis symptoms will be requested to report to the study site/clinic for a scheduled or unscheduled visit, during which clinical assessments will be performed to gather all the necessary diagnostic data to confirm or rule out the presence of pericarditis recurrence (Section 6.1.4). The Investigator will evaluate all assessments performed for a diagnostic workup, whether at the study site or at locations outside.

Upon completion of pericarditis workup, the Investigator is required to contact the [REDACTED] [REDACTED] medical monitor to confirm that the protocol required diagnostic workup is complete prior to implementing treatment for the event.

[figure not shown]
Following communication with the [REDACTED] medical monitor, if the event meets the criteria for bailout riloncept (at least 1 day with pericarditis pain measurement ≥ 4 on the 11-point NRS and one CRP value ≥ 1 mg/dL either on the same day or separated by no more than 7 days), and after the [REDACTED] medical monitor has confirmed with the Investigator that the diagnostic workup is complete, the attainment of bailout criteria is confirmed in the IWRS, blinded study drug is discontinued, and open-label riloncept treatment is dispensed. If needed, sequential ORT is allowed as outlined in Section 5.6.3. The subject will continue to be followed up according to Section 13.1 for the RW period.

Following communication with the [REDACTED] medical monitor, if the event does not meet the protocol criteria for bailout riloncept but in the judgement of Investigator requires treatment, after the [REDACTED] medical monitor has confirmed with the Investigator that the diagnostic workup is complete, the Investigator is allowed to add sequential ORT to blinded study drug, and as outlined in Section 5.6.3. Blinded study drug treatment will continue until a pericarditis recurrence that meets criteria for bailout riloncept, or until the end of the RW period.

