7.7.3. Testing Hypotheses and Multiplicity Adjustment

All statistical tests for the treatment comparison of efficacy endpoints in the RW period will be based on the ITT analysis set with 1-sided $\alpha=0.025$ unless otherwise specified. For each endpoint, the null hypothesis is that the effects of rilonacept and placebo are the same. The alternative hypothesis is that rilonacept is better than the placebo.

In order to control the overall 1-sided type I error rate at the 0.025 level, a gatekeeping procedure in combination with Hochberg's procedure will be applied to testing the primary and major secondary endpoints. If the 1-sided p-value for testing the primary endpoint is ≤ 0.025 , a significant treatment effect on the primary endpoint will be claimed.

Section 7.2.1 provides the order of major secondary endpoints. If the primary endpoint is significant, the first major secondary endpoint, i.e., proportion of subjects who maintained Clinical Response at Week 24 of RW period will be tested at 1-sided $\alpha=0.025$. A significant treatment effect on this major secondary endpoint will be claimed if the 1-sided p-value is ≤ 0.025 . If the treatment effect is not significant on the primary endpoint, significance on this major secondary endpoint cannot be claimed regardless of the result.

If both primary and first major secondary endpoints are significant following the above procedure, the second and third major secondary endpoints defined in Section 7.2.1 will be tested with Hochberg's procedure at overall 1-sided $\alpha=0.025$. If both 1-sided unadjusted

p-values are ≤ 0.025 , claim significance of rilonacept for both endpoints. If the larger 1-sided p-value is > 0.025 , compare the smaller 1-sided p-value with 0.0125. If the smaller 1-sided p-value is ≤ 0.0125 , claim significance of rilonacept on this endpoint.

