7.7.5. Analysis of Secondary Efficacy Endpoints

7.7.5.1. Analysis of the Major Secondary Endpoints

The analyses for the 3 major secondary endpoints will be based on the ITT Week 16 analysis set, with the Week 8 and Week 24 ITT analysis sets providing supportive sensitivity analyses.

- Proportion of subjects who maintained Clinical Response at Week 16 of the RW period (defined as a weekly average of daily pericarditis pain ≤ 2.0 on the 11-point NRS, CRP ≤ 0.5 mg/dL, and on monotherapy of randomized study drug at Week 24). The Cochran–Mantel–Haenszel (CMH) test will be used in this analysis, stratified by the stratification variables for randomization.
- Percentage of days with no or minimal pain in the first 16 weeks post randomization. Minimal or no pain is defined as non-missing daily NRS ≤ 2 on the 11-point NRS. This endpoint will be analyzed with an analysis of covariance. In addition to treatment arm, the following covariates will be included in this analysis: the stratification variables for randomization, and RI baseline NRS weekly average in 2 categories: NRS ≤ 2 versus NRS > 2 .
- Proportion of subjects with absent or minimal pericarditis symptoms (based on the 7-point PGIPS) at Week 16 of the RW period. The CMH test will be used in this analysis, stratified by the stratification variables for randomization.

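### The gatekeeping responder rule reads status at the visit only, so a subject with an earlier confirmed recurrence and completed oral rescue can count as having maintained Clinical Response

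*Protocol*

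**What the plan says.** All references are to Protocol Version 3.0 (Amendment 2).

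Section 7.2.1 names the first major secondary endpoint as the proportion who maintained Clinical Response at Week 16. It requires a weekly mean NRS of at most 2.0, CRP of at most 0.5 mg/dL, "and on monotherapy of randomized study drug at Week 16". Section 7.7.5.1 repeats the conditions as the meaning of maintained response but ends "and on monotherapy of randomized study drug at Week 24". Section 7.7.3 also still names Week 24 for this endpoint. The Week 8 and Week 24 versions in 7.2.2 use the same idea.

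Section 7.7.3 makes the endpoint a gate. The other two major secondaries are tested by Hochberg's procedure only on this condition: "If both primary and first major secondary endpoints are significant following the above procedure".

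Section 6.2.3 describes a recurrence as "defined as the recurrence of typical pericarditis pain associated with supportive objective evidence of pericarditis". The pair NRS ≥4 and CRP ≥1 mg/dL is the bailout criterion, not part of that definition. For events below it, section 3.1.3 says: "Subjects with pericarditis recurrence who do not meet the protocol criteria for bailout rilonacept will continue blinded study drug". Section 6.2.3 adds that "the Investigator is allowed to add sequential ORT to blinded study drug". For an event that meets the bailout criteria, section 5.7 says that "the subject will be transitioned to open-label rilonacept".

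**The concern.** The word maintained suggests response held from randomization to the visit. The conditions test only how the subject stands at the visit. The protocol plans for a route by which the two part company: a recurrence that the Clinical Endpoint Committee (CEC) confirms, that does not reach the bailout thresholds, and that is handled with oral rescue on top of blinded drug. No section requires that rescue to last until any given visit. Once it has stopped and pain and CRP are low, every condition is met.

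The same subject is a failure for the primary endpoint in 7.1. The recurrence-free proportion in 7.2.2 does not repair this, because it is read at 24 weeks and lies outside the gatekeeping. At stake are what the gating endpoint means and its power, and through the gate the chance of testing the other two major secondaries at all.

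**Working it through.** **1. Who passes the rule after a recurrence.**
- Bailout rilonacept: no longer on randomized drug, so fails.
- Corticosteroids needed: blinded drug is discontinued (5.6.3), so fails.
- Still taking NSAID or colchicine rescue at the visit: not on monotherapy, so fails.
- Confirmed recurrence below bailout, rescue finished, weekly NRS ≤2.0 and CRP ≤0.5 mg/dL at the visit: passes.

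Only the last group is misclassified.

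**2. The plan's own figure.** Inputs from 7.4: one-sided 2.5%, power 90%, exponential times, placebo median 8 weeks, hazard ratio 0.244, 1:1 allocation. Schoenfeld: (1.960 + 1.282)² / (0.25 × (ln 0.244)²) = 21.12, rounded up to the stated 22 events. Power with 22 events is 91.1%. Randomizing 50 with 10% run-in loss gives 50 / 0.90 = 55.6, hence the stated 56. The planning inputs are reproduced. The protocol gives no power for the Week 16 responder endpoint.

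**3. Recurrence by Week 16 on those inputs.**
- Placebo recurrence-free: exp(−ln 2 × 16/8) = 0.250, so 75.0% recur.
- Rilonacept recurrence-free: exp(−0.244 × ln 2 × 16/8) = 0.713, so 28.7% recur.
- Difference if every recurrence is a non-response and every recurrence-free subject responds: 0.713 − 0.250 = 0.463.

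**4. Effect of the visit-status rule.** Let f be the share of recurrences that end in the passing group of step 1. The protocol gives no value, so f is an assumption. With the same f in both arms, the responder proportion is S + f(1 − S), where S is the recurrence-free proportion, and the difference becomes 0.463 × (1 − f). Power is for an unstratified comparison of two proportions, 25 per arm, one-sided 0.025.

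| f (assumed) | Placebo | Rilonacept | Difference | Power | Misclassified per 25, placebo / rilonacept |
|---|---|---|---|---|---|
| 0 | 25.0% | 71.3% | 46.3 points | 93% | 0 / 0 |
| 10% | 32.5% | 74.2% | 41.7 points | 86% | 1.9 / 0.7 |
| 20% | 40.0% | 77.0% | 37.0 points | 77% | 3.8 / 1.4 |
| 30% | 47.5% | 79.9% | 32.4 points | 67% | 5.6 / 2.2 |

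Placebo gains more responders because it has more recurrences to reclassify.

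**The case against.** The best defence is that the remaining path is narrow and the endpoint legitimate. The event must be confirmed, must miss bailout and not reach it later, and must have settled with rescue stopped. How rescue is used is left to the Pharmacy Manual and how events are confirmed to the CEC charter, so its frequency cannot be read from the protocol. A state-at-visit endpoint is a reasonable choice; the PGIPS endpoint in the same family is one. Freedom from recurrence is already the primary endpoint, and requiring it here makes the two overlap more. All of this stands as a limit on size. It does not remove the mismatch between the label and the rule. Nor is this a detail left to the SAP, because the protocol itself fixes the responder conditions.

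A reader might infer more than the text supports, in three ways.
- *That anyone given oral rescue can still count.* Ongoing NSAID or colchicine use fails the monotherapy condition; only completed rescue passes.
- *That misclassification favours rilonacept, because bailout depends on CRP and the drug suppresses CRP.* Section 3.3 expects that the dose "will consistently provide adequate suppression of clinical inflammatory response, including CRP levels", which reads as disease control, not as a masked marker during an active recurrence. Bailout also needs NRS ≥4. On the planning model, 54% of rilonacept recurrences by Week 16 fall by Week 8 (0.156/0.287), against 67% on placebo (0.50/0.75), so there would be less time on rilonacept to recover and stop rescue. The direction of any arm difference is unknown.
- *That type I error is inflated.* If treatment has no effect and f is equal, the responder proportions are equal and the test is not biased.

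**Conclusion.** The point holds as a defect in a stated rule at the gatekeeping endpoint. As written, a subject can have maintained Clinical Response and also be an event in the primary analysis, and nothing elsewhere in the protocol prevents it. The consequence that can be supported is dilution: for an assumed 10% to 30% of recurrences in both arms, the difference falls from about 46 points to between 42 and 32, and power from about 93% to between 86% and 67%.

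These figures rest on the exponential planning assumptions in 7.4, on every recurrence-free subject responding, on all 25 per arm entering the ITT Week 16 set (which could be smaller), and on a share f that the documents do not give. A claim of bias between arms would be speculation. The matter should be corrected, but it does not threaten the primary analysis.

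**What to change.** In 7.2.1 and 7.7.5.1, and for the Week 8 and Week 24 versions, state for the analysis that a subject is a non-responder if, between randomization and that visit, there was a CEC-confirmed recurrence, NSAID, colchicine or corticosteroid use for pericarditis, or bailout rilonacept. State also that analgesic use alone, during work-up of an event the CEC does not confirm, is not a non-response. That clause is needed because oral rescue includes analgesics and 5.6.3 allows them before the work-up is complete. Keep the visit-status version as a supportive summary. Correct the leftover Week 24 to Week 16 in 7.7.3 and in the definition in 7.7.5.1.

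This changes scoring only, not how recurrences are treated. It needs no new data: recurrences are adjudicated (6.7.2), and oral rescue, prednisone and bailout use are already summarized cumulatively every 4 weeks (7.2.2). The cost is lower responder rates in both arms, more so on placebo (at f = 20%, from 40.0% to 25.0%, against 77.0% to 71.3% on rilonacept), and more overlap with the primary endpoint. Renaming the endpoint as being in Clinical Response at Week 16 would mend the label but leave the dilution at the gate.

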6.2.1.5. Patient Global Impression of Pericarditis Severity

Patient Global Impression questionnaires have been developed for a variety of indications. The PGIPS is a single-item PRO measure that assesses the subject's impression of overall severity of pericarditis symptoms at the time the questionnaire is administered, using a 7-point rating scale ranging from absent (no recurrent pericarditis symptoms) to very severe (recurrent pericarditis symptoms cannot be ignored) (Guy 1976). The PGIPS can be completed in less than 30 seconds.

The subject will select from the following that best describes the severity of pericarditis symptoms at the time of occurrence of the event:

- Absent: no symptoms
- Minimal: can be easily ignored without effort
- Mild: can be ignored with effort

- Moderate: cannot be ignored but does not influence my daily activities
- Moderately severe: cannot be ignored and occasionally limits my daily activities
- Severe: cannot be ignored and often limits my concentration on daily activities
- Very severe: cannot be ignored and markedly limits my daily activities

The PGIPS will be collected as described in Section 13.1.

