7.4. Sample Size Calculations

For the purpose of sample size estimation, time to pericarditis recurrence is assumed to follow an exponential distribution. An event of interest is defined as a subject's first adjudicated recurrence of pericarditis. The following assumptions are used in the sample size calculation using EAST 6.4.1:

- 1-sided significance level 2.5%
- Power 90%
- Median time to event (in weeks) in placebo 8
- Hazard ratio (rilonacept/placebo) 0.244
- Percentage of subjects in the RI period that will not reach RW 10%

Given these assumptions, a total of 22 adjudicated pericarditis recurrence events is required to achieve the power. About 25 subjects per arm (a total of 50 subjects) will be randomized. Considering 10% of subjects in the RI period that will not reach the RW period, approximately 56 subjects will be enrolled in this study.

Patient enrollment and the pericarditis recurrence event accrual will be closely monitored during the study. The monitoring activities will be done in a blinded fashion during the RW period. If the number of patients randomized is less than 50 and/or the time anticipated for the number of events required for the analysis of primary efficacy endpoint significantly exceeds the projected timeline, additional patients may be enrolled and/or randomized at Kiniksa Pharmaceutical's discretion. However, at this time it is anticipated that no more than 100 subjects will be enrolled into this study.

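### Major secondary endpoints 2 and 3, unlike endpoint 1, carry no randomized-drug condition, so as written they credit scores on open-label bailout rilonacept to the randomized arm and shrink the treatment difference

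*Protocol*

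**What the plan says.** All references are to Protocol Version 3.0 unless stated.

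- **Endpoint definitions.** Section 7.2.1 lists three major secondary endpoints. Endpoint 1, Clinical Response at Week 16, includes being on monotherapy of randomized drug. Endpoint 2 is described in Section 7.7.5.1 as "Percentage of days with no or minimal pain in the first 16 weeks post randomization", with a pain-free day defined only by a non-missing NRS ≤2. Endpoint 3 is the "Proportion of subjects with absent or minimal pericarditis symptoms (based on the 7-point PGIPS) at Week 16 of the RW period". Neither section gives endpoint 2 or 3 a condition on current treatment.
- **Bailout.** Under Section 3.1.3, a recurrence with NRS ≥4 and CRP ≥1 mg/dL leads to open-label rilonacept "irrespective of randomized treatment assignment and as soon as at least 5 days have passed since the last study drug injection". Recurrences that do not meet both criteria stay on blinded drug, with oral rescue therapy (ORT) if needed.
- **Follow-up and analysis.** Section 6.2.3 keeps bailed-out subjects on the randomized-withdrawal schedule. Table 3 in Section 13.1 has daily NRS throughout and PGIPS at Week 16. Section 7.5 places everyone randomized at least 16 weeks before cutoff in the ITT Week 16 set, and ITT comparisons follow randomized assignment.
- **Multiplicity.** Section 7.7.3 tests endpoints 2 and 3 by Hochberg's procedure once the primary endpoint and endpoint 1 have succeeded.
- **PGIPS reference time.** Section 6.2.1.5 first says the PGIPS reflects severity when the questionnaire is given. It then tells the subject to choose the category "that best describes the severity of pericarditis symptoms at the time of occurrence of the event".

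**The concern.** Rescue here is the test drug itself. A placebo subject who recurs, receives bailout rilonacept and is well by Week 16 meets the definition of a placebo responder on endpoint 3, and the good days after bailout count for placebo on endpoint 2. The comparison becomes continued rilonacept against placebo followed by rilonacept when needed. Endpoint 1, in the same list, avoids this.

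The scores in question are observed, so Section 7.7.1's deferral of missing-value handling to the SAP does not reach them. Section 7.7.5.2 concedes that recurrence could bias the repeated-measures comparisons, but Section 7.7.5.1 has no such caveat for the major secondary endpoints.

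At stake are two alpha-controlled claims that could be lost although rilonacept works as assumed, and estimates that do not describe withdrawal against continuation.

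**Working it through.** **Inputs from Section 7.4:** exponential times; "1-sided significance level 2.5"%; 90% power; "Median time to event (in weeks) in placebo 8"; "Hazard ratio (rilonacept/placebo) 0.244"; about 25 randomized per arm.

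**The plan's own figure.** Schoenfeld events = 4(1.960 + 1.282)² / (ln 0.244)² = 21.1, rounded up to 22. This agrees with the statement that "a total of 22 adjudicated pericarditis recurrence events is required to achieve the power".

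**Recurrence by Week 16**
- Placebo: 1 − 2^(−16/8) = 0.750.
- Rilonacept: 1 − 2^(−0.244 × 16/8) = 0.287.

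**Endpoint 3.** The documents do not give the following, so they are assumed:
- b, share of recurrences that go to bailout: 0.5 to 1.
- r, share absent/minimal on PGIPS after bailout: 0.5 to 0.95.
- u, share absent/minimal after recurrence without bailout: 0.3.
- Subjects without recurrence: all absent/minimal.

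As-observed responder rate = S(16) + [1 − S(16)] × [b·r + (1 − b)·u], where S(16) is 0.250 for placebo and 0.713 for rilonacept. Power is for an unstratified Mantel-Haenszel test, by enumeration, at one-sided 0.025 with 25 per arm.

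| Scoring | Placebo | Rilonacept | Difference (points) | Power |
|---|---|---|---|---|
| Recurrence = failure | 25.0% | 71.3% | 46.3 | 94% |
| As observed, b=0.5, r=0.5 | 55.0% | 82.8% | 27.8 | 59% |
| As observed, b=0.75, r=0.7 | 70.0% | 88.5% | 18.5 | 39% |
| As observed, b=1, r=0.8 | 85.0% | 94.3% | 9.3 | 18% |
| As observed, b=1, r=0.95 | 96.2% | 98.6% | 2.3 | 1% |

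Even the most favourable as-observed case loses 94 − 59 = 35 points of power. The last row is very low partly because the test is discrete when both rates are near 100%; a normal approximation gives 7%. If only 90% of subjects without recurrence are absent/minimal, the failure-scored rates are 22.5% and 64.2%, a difference of 42 points.

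**Endpoint 2.** If every day after recurrence counts as not pain-free, the expected share of good days is (1 − e^(−16λ))/(16λ), with 16λ = 1.386 for placebo and 0.338 for rilonacept:
- Placebo: 0.750/1.386 = 54.1%.
- Rilonacept: 0.287/0.338 = 84.8%.
- Difference: about 31 points, or 0.95 × 30.7 = about 29 if 95% of other days are pain-free.

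As observed, a recurrence costs only its painful days D (assumed 5 to 28). The difference is about (0.750 − 0.287) × D/112: 2.1 points for D=5 and 11.6 for D=28. Truncating late recurrences at Day 112 and using 95% pain-free days elsewhere gives 2.0 and 10.6 points.

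Power for endpoint 2 depends on an unstated between-subject SD. With an added SD of 15 to 20 points (assumed), it is about 5% to 54% as observed, against 80% to 86% with post-recurrence days as failures. With no added SD it stays near 95% even as observed, so for this endpoint the shrunken estimate is the firmer result.

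**The case against.** **The protocol is silent.** It never says in words that scores after bailout count. Section 7.7 leaves methods and data conventions to the SAP, and the SAP could set a rule. That is fair as far as it goes. But the endpoint definitions are fixed in this document and address current treatment for one endpoint out of three. A SAP rule would change a definition rather than fill in a missing value.

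**Treatment policy is a legitimate estimand.** Analysing observed scores by randomized arm is not in itself an error. This stands. The objection here is that the list mixes two strategies without saying so, in a design where rescue is the test drug.

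**The composite has its own weakness.** Counting rescue days as failures overrides recorded low scores and brings endpoint 2 close to time to recurrence. This also stands, and it is a cost of the fix.

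**Stronger readings that the documents do not support**
- A reader might infer that most placebo subjects are on active drug at Week 16. With 75% recurring, this needs more than 0.50/0.75, about two thirds, of recurrences to qualify for bailout. No such share is given, and recurrences below the criteria stay on blinded drug.
- A reader might infer that the difference falls to near zero. For PGIPS that needs almost every recurrence bailed out and recovery almost equal to that of subjects who never recurred.
- A reader might treat endpoint 2 as a Week 16 reading. It accumulates over 16 weeks, so flare days still count against placebo.

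**Conclusion.** The point holds as an inconsistency among the endpoint definitions with a material effect on power and interpretation. Read as written, endpoints 2 and 3 credit scores on open-label rilonacept to the randomized arm.

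For endpoint 3, at 25 per arm, the difference drops from about 46 points (94% power) to about 2–28 points (1% to 59%). For endpoint 2 it drops from about 29–31 points to about 2–11. The recurrence rates follow from Section 7.4; bailout share, recovery, well-being without bailout and painful days per recurrence are assumed ranges. The 46-point figure treats every recurrence as failure, so it applies in full only if each one leads to bailout or other rescue. About 29% of the rilonacept arm also recurs, and the calculation allows for this.

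Severity is should-fix. A reader might infer that the trial's main claim is at risk. It is not: the primary endpoint and endpoint 1 are untouched, endpoints 2 and 3 are tested only after both succeed, and dilution toward the null risks lost claims rather than false ones.

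The two PGIPS reference times are a separate contradiction that needs no assumptions. It has no quantified effect and does not raise the severity.

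**What to change.** In Sections 7.2.1 and 7.7.5.1, before unblinding:

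- **Endpoint 3:** count a subject who is not on monotherapy of randomized study drug at Week 16 as a non-responder, as endpoint 1 does. Take the Week 16 time point from Section 7.2.1; the matching clause in Section 7.7.5.1 says Week 24 and should be aligned.
- **Endpoint 2:** count days from the start of bailout rilonacept, corticosteroids or ORT for recurrence as not no/minimal pain.
- Use one list of rescue treatments for both endpoints, and say how a completed ORT course is treated.
- Apply the same rules to the Week 8 and Week 24 versions, and keep the as-observed results as sensitivity analyses.
- In Section 6.2.1.5, reconcile the two PGIPS reference times.

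The cost is wording in the protocol and SAP. No new data are needed, since concomitant medication is recorded and Section 7.2.2 already tabulates ORT, prednisone and bailout use every 4 weeks. The downside is that both endpoints become composites of symptoms and rescue and overlap more with the primary endpoint, which is why the as-observed versions should still be reported.
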